Demographic information on the participants age, race, gender, seizure frequency, medications, history of epilepsy surgery, employment status, address, and distance from the exercise facility will be recorded on all screened subjects. If eligible and willing to participate, the email and/or mailing address will be recorded in order to mail or email a copy of the consent form for optional review prior to the enrollment visit. For ineligible participants, the reason(s) for ineligibility will be recorded. For eligible participants who decline to participate, we will also record the reason for declining.

- Chart review study: Potentially eligible subjects have been identified through a recently conducted chart review (IRB00056209). This database contains over 800 charts from approximately April to October 2018 at WFBH Adult Epilepsy Clinic. Charts have been screened for seizure frequency, cognitive level and ambulatory status. Preliminarily eligible patients may be contacted via the procedures described above.
- Cross-sectional survey: Potentially eligible subjects have been identified through a recently conducted survey (IRB00062580) in the WFBH Adult Epilepsy Clinic and the adult Epilepsy Monitoring Unit (EMU). Participants were surveyed regarding their seizure frequency, baseline activity habits, and interest and ability to participate in a monitored physical activity intervention. They also indicated their willingness to be contacted for future studies. Preliminarily eligible patients may be contacted via the procedures described above.
- Observational survey: Potentially eligible subjects will be identified through a recently conducted observational study (IRB00062034) using wearable devices to track activity and sleep in epilepsy. In this study they also indicated their willingness to be contacted for future studies. Preliminarily eligible patients may be contacted via the procedures described above.
- Prior pilot study: (IRB00068408) participants who were screened for this study but were not eligible or did not enroll will be identified from the existing screening database and examined for eligibility. Preliminarily eligible patients may be contacted as described above.
- Further eligible participants will be identified by prospective chart review of all epilepsy patients presenting to the adult epilepsy clinic each week for outpatient appointments (in-person or telehealth) or epilepsy monitoring unit admissions. We will review the chart for eligibility. Preliminarily eligible patients may be approached in clinic by a member of the study team and screened for eligibility or contacted via the procedures described above. Any potentially eligible participants communicated to the study team via word of mouth may also be contacted as described above.

Eligible subjects who agree to participate will be scheduled for V1 Enrollment. They will be mailed or emailed a copy of the consent form and a study overview handout (attachment 3) to review prior to enrollment.

In addition, the study will be added to the “Be Involved” website of WFBMC with contact information of the study staff. Interested participants who email or call will undergo the telephone screening process described above. Informational flyers will be hung in each room in the adult epilepsy clinic (again with contact information), inpatient Epilepsy Monitoring Unit, and displayed at the monthly epilepsy support group meetings. Lastly, an informational flyer with contact information will be posted on the Epilepsy Alliance of North Carolina’s website. Flyers may also be distributed throughout the community and at other health clinics in the surrounding areas.

Informed Consent

Signed informed consent will be obtained from each subject. Consent will be obtained by a

Protocol version:

Template updated 9.24.14

member of the study staff at the enrollment visit. Those who are scheduled for an enrollment visit will be mailed and/or emailed a copy of the informed consent document for optional reading prior to enrollment.

Confidentiality and Privacy

Confidentiality will be protected by collecting only information needed to assess study outcomes, minimizing to the fullest extent possible the collection of any information that could directly identify subjects, and maintaining all study information in a secure manner. To help ensure subject privacy and confidentiality, only a unique study identifier will appear on the data collection form. Any collected patient identifying information corresponding to the unique study identifier will be maintained on a linkage file, stored separately from the data. The linkage file will be kept secure, with access limited to designated study personnel. Following data collection subject identifying information will be destroyed 6 years after study completion by deleting the linkage file, consistent with data validation and study design, producing an anonymous analytical data set. Data access will be limited to study staff. Data and records will be kept locked and secured, with any computer data password protected. No reference to any individual participant will appear in reports, presentations, or publications that may arise from the study.

In group meetings with participants, respect for the privacy and confidentiality of other group attendees will be emphasized.

Data and Safety Monitoring

The principal investigator will be responsible for the overall monitoring of the data and safety of study participants. The principal investigator will be assisted by other members of the study staff. A Data Safety and Monitoring Committee, an independent group of experts, will be reviewing the data from this research throughout the study

Reporting of Unanticipated Problems, Adverse Events or Deviations

Any unanticipated problems, serious and unexpected adverse events, deviations or protocol changes will be promptly reported by the principal investigator or designated member of the research team to the IRB and sponsor or appropriate government agency if appropriate.

SAFETY AND MONITORING PLAN

Adverse Event Definitions:

Adverse Event: (AE) For the purposes of this trial an adverse event is defined as any untoward or unfavorable medical occurrence that is temporally associated with the subject's participation in the research, whether or not considered related to the subject's participation in the research.

Expected Events: In this study, no serious adverse events are expected. Expected adverse events include temporary muscle soreness, temporary joint pain, and temporary increased physical fatigue when starting the exercise regimen or when increasing the exercise. Other expected events include mild discomfort from physical exertion including shortness of breath that improves when ceasing exercise and sweating. In people with asthma, an increase in the need for inhaler use is expected. In people who have a very high baseline seizure frequency, and even in those with less frequent seizures, seizures are reasonably expected to occur during exercise on occasion and certainly will occur during the course of the study. However, seizures that occur consistently with exercise in a single individual is not expected. In addition, it is not expected for participants to have a large

Protocol version:

Template updated 9.24.14

increase in seizure frequency. A small increase would be within the normal fluctuation of seizure frequency in people with epilepsy.

Specifically, the temporal relationship of seizures to exercise will be recorded in the daily study diary. Responses will be reviewed by the study team weekly. In participants who demonstrate an increase in seizure frequency from their baseline weekly frequency consistently over a 4 week period, the temporal relationship to exercise will be further investigated. In those who have increased seizure frequency AND who report a clear temporal association with exercise (seizure occurs during or immediately after exercise in 50% or more of their seizures), participation in the intervention will be halted due to concern for exercise-induced seizure activity.

All other events not listed above will be considered unexpected for the purposes of this trial. The unblinded investigator will be responsible for determining whether an AE is expected or unexpected. An AE will be considered unexpected if the nature, severity, or frequency of the event is not consistent with the risk information previously described for the study intervention.

Adverse Event Classification:

All AEs will be assessed by the study staff for severity and categorized using the criteria described below.

Serious Adverse Events: (SAE) Any event that results in death, hospitalization or prolongation of a hospitalization, significant or persistent disability, a birth defect or congenital anomaly, or another significant event or problem requiring medical or surgical intervention to prevent one or more of the above.

General Adverse Events:

Mild Adverse Events: Events that require minimal or no treatment and do not interfere with the participant's daily activities.

Moderate Adverse Events: Events result in a low level of inconvenience or concern with the therapeutic measures. Moderate events may cause some interference with functioning.

Severe Adverse Events: Events that interrupt a participant's usual daily activity and may require systemic drug therapy or other treatment. Severe events are usually potentially life-threatening or incapacitating. Of note, the term "severe" does not necessarily equate to "serious".

All adverse events will also have their relationship to study intervention assessed by one of the co-investigators (un-blinded) who will examine and evaluate the participant based on temporal relationship and his/her clinical judgment and categorized into one of the following:

Definitely Related: There is clear evidence to suggest a causal relationship, and other possible contributing factors can be ruled out. The clinical event, including an abnormal laboratory test result, occurs in a plausible time relationship to study intervention administration and cannot be explained by concurrent disease or other drugs or chemicals. The response to withdrawal of the study intervention (dechallenge) should be clinically

plausible. The event must be pharmacologically or phenomenologically definitive, with use of a satisfactory rechallenge procedure if necessary.

Probably Related: There is evidence to suggest a causal relationship, and the influence of other factors is unlikely. The clinical event, including an abnormal laboratory test result, occurs within a reasonable time after administration of the study intervention, is unlikely to be attributed to concurrent disease or other drugs or chemicals, and follows a clinically reasonable response on withdrawal (dechallenge). Rechallenge information is not required to fulfill this definition.

Potentially Related: There is some evidence to suggest a causal relationship (e.g., the event occurred within a reasonable time after administration of the trial medication). However, other factors may have contributed to the event (e.g., the participant's clinical condition, other concomitant events). Although an AE may rate only as "possibly related" soon after discovery, it can be flagged as requiring more information and later be upgraded to "probably related" or "definitely related", as appropriate.

Unlikely to be related: A clinical event, including an abnormal laboratory test result, whose temporal relationship to study intervention administration makes a causal relationship improbable (e.g., the event did not occur within a reasonable time after administration of the study intervention) and in which other drugs or chemicals or underlying disease provides plausible explanations (e.g., the participant's clinical condition, other concomitant treatments).

Not Related: The AE is completely independent of study intervention administration, and/or evidence exists that the event is definitely related to another etiology. There must be an alternative, definitive etiology documented by the clinician.]

Adverse Event Tracking:

Adverse Events that are of special interest for this study will be actively tracked. These include worsening of seizure frequency, falls, and injuries. These will be specifically recorded by the participant in their study diary, which will be returned electronically daily.

All other adverse events will be passively collected at each study visit (visits 2-4) by asking "have you had any health problems since your last visit?"

All AEs will be captured on the appropriate case report form (CRF). Information to be collected includes event description, time of onset, clinician's assessment of severity, relationship to study intervention (assessed only by those with the training and authority to make a diagnosis), and time of resolution/stabilization of the event. All AEs occurring during the study must be documented appropriately regardless of relationship.

Any medical condition that is present at the time that the participant is screened will be considered as baseline and not reported as an AE. However, if the study participant's condition deteriorates at any time during the study, it will be recorded as an AE.

Management of Suicidal Ideation:

Given the nature of NDDI-E as a depression screening tool, question 4 pertains to passive suicidality. If participants score a 3 or 4 on this question, follow-up questions will be carried out by study staff, to determine any possibility of active suicidality. If there is a need for immediate treatment (e.g., active suicidal ideation, active psychotic symptoms, disorientation, active substance abuse) at any point in time, staff will follow the in-person crisis procedures included in Appendix A. If, during a remote visit, a participant voluntarily expresses suicidal ideation, we will follow the established crisis procedures under the remote protocol in Appendix A. Follow-up questions and any immediate treatments will be documented in the "Review Assurance of the NNDI-E" form.

As a safety precaution, we will ask each participant upon study enrollment to identify 1 persons whom we can contact in case of an emergency and provide a telephone numbers for this individual.

If suicidality is expressed, we may notify their outpatient neurologist in order to help guide future care.

Because this is not a treatment study, and given the low rate of active suicidality previously identified during a Wake Forest Baptist Health learning health system trial led by [name] (included screening more than 760 individuals using the NDDI-E instrument), we anticipate that active suicidality will be exceedingly rare. All study staff will receive training on the crisis protocol and will have regular meetings with the team to discuss clinical issues.

Management of Seizures:

The principal investigator will provide training to all study staff regarding seizure management and seizure first aid. Staff will be informed the proper way to care for the patient during the acute seizure period including how to keep the patient from injuring themselves, how to time a seizure, and when to call for help. The PI will be notified in all instances to provide further guidance. Staff will follow outlined safety procedures on when and how to contact any necessary additional emergency care. It should be noted that most seizures do NOT require emergency care and will resolve on their own, but staff will be trained to respond to all scenarios. Participants will always be advised to notify their primary outpatient epilepsy physician of any seizures and this provider will guide long-term management of their care.

References

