- Focal or generalized epilepsy, as determined clinically by a WFBH epileptologist with no significant consideration of an alternative diagnosis
- Active epilepsy with at least 1 observable seizure in the 6 months prior to screening
- Access to a smartphone with application capabilities
- Internet access or cellular data plan to attend virtual sessions
- Able to ambulate independently

Exclusion Criteria

- Diagnosis of nonepileptic or psychogenic spells
- Seizures associated with falls with injury (such as atonic seizures)
- Currently active ≥ 30 min on 3 or more days per week or > 5000 steps/day during the baseline period
- Medical conditions that would limit ability to participate in an exercise intervention including:
 - Stage III or IV Congestive Heart Failure (CHF)
 - End-stage Renal Disease
 - Severe dementia or significant cognitive impairment that precludes participation in the intervention or limits ability to follow the study protocol
 - Uncontrolled hypertension (HTN) defined as systolic blood pressure greater than 180 mmHg and diastolic blood pressure greater than 110 mmHg at rest
 - Severe arthritis, amputations, or orthopedic problems that limit ambulatory ability
- Currently pregnant or plan to become pregnant during the study period (16 weeks)
- An active Central Nervous System (CNS) infection, demyelinating disease, degenerative neurologic disease or any CNS disease deemed to be progressive during the course of the study that may confound the interpretation of the study results
- Any clinically significant psychiatric illness, psychological, or behavioral problems that would interfere with the subject's ability to participate in the study.
- Unwilling or unable to comply with all study visits and procedures
- Participants who have $<75\%$ complete days of seizure recording in the study diary or step data via the Garmin device will not be randomized.

Sample Size

Up to 40 subjects will be enrolled, with a 2:1 ratio of intervention to control group randomization to best address aims 1 and 2.

Interventions and Interactions

Protocol version:

Template updated 9.24.14

All participants will wear a Garmin device and keep a study diary throughout the duration of the study. In addition, they will wear an ActivPAL 4 for 1 week at the end of the baseline, intervention, and maintenance periods. This will be mailed to them for each of the three recording periods along with written instructions (attachment 8).

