Questionnaires: PSS, AEP, NDDI-E, Review Assurance of the NNDI-E, GAD-7, QOLIE-31, EXSE, EGS, MOESS, LSSS		X				X	X (with exception of NNDI-E and "Review Assurance of the NNDI-E")
HRV measurement		X	X			X	
6 minute walk test		X				X	
Exit Questions							X

*in addition to review at these visits, the study diary will also be returned daily and reviewed by weekly by a member of the study staff.

**If scheduling is a challenge, V2 can be completed over the telephone with the exercise test being conducted at the first available timepoint and prior to the intervention period

Outcome Measure(s)

1. Primary Objective: Feasibility of the intervention (Adherence and Sustainability)
 - a. Primary Endpoints
 - i. Adherence to the intervention
Adherence will be measured as the number of average daily steps achieved compared to steps assigned during the final 4 weeks of the intervention period
 - ii. Sustainability of the intervention
Sustainability will be measured as the number of average daily steps achieved compared to steps assigned during the final 4 weeks of the maintenance period
2. Secondary Objectives: To evaluate the intensity distribution in the intervention arm
 - a. Secondary Endpoints: time spend in various activity behaviors (measured by the ActivePAL4)
 - i. Time spent sedentary
 - ii. Time spent in light intensity activity
 - iii. Time spent in moderate intensity activity
 - iv. Time spent in vigorous intensity activity
 - v. Acceptability of the Intervention
Participants will answer an exit survey at Visit 4 regarding what they liked about the study and what they did not like, including reasons for missed visits or non-adherence, barriers encountered, and overall satisfaction of various aspects of the study. In addition, arm 1 will answer a questionnaire at the end of the 12 week intervention about the acceptability, tolerance and satisfaction

Protocol version:

Template updated 9.24.14

with the exercise intervention. For the main endpoint, we will use the question “How satisfied were you with the exercise intervention?” with scale of 1=VERY UNSATISFIED, 2=UNSATISFIED, 3=NEUTRAL, 4=SATISFIED, 5=VERY SATISFIED. We will calculate the proportion of subjects who answer 4 or above.

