Efficacy Questionnaire (EXSE)[51], Exercise Goal Setting Questionnaire (EGS)[52], and Multidimensional Expectations for Exercise Scale (MOEES)[53]. These will be given in person at Visits 1 and 3 and remotely via redcap survey at Visit 4.

2.

v. Effects on physical function

1. Autonomic tone: Heart rate variability (HRV)

a. Heart Rate Variability (HRV) measurement: Continuous heart rate will be recorded while the participant is breathing normally in seated position for 10 minutes using Faros 180 heart rate monitor (Bittium Corporation, Oulu, Finland)[54]. Beat to beat intervals (RRI) files will be generated at 1000 Hz via the data acquisition software. The files will be analyzed with Nevrokard HRV software (by Nevrokard Kiauta, d.o.o., Izola, Slovenia). The recordings will be visually inspected to ensure data quality (dropped beats or gross motion artifacts are excluded) and the first 5 minutes of usable tracings will be analyzed. We will obtain measures of HRV in the frequency domain and these measures will be integrated over specified frequency ranges (LF: 0.04-0.15 Hz; HF: 0.15-0.4 Hz). Power of RRI spectra in LF, HF range (LFRRI and HFRRI) will be calculated in normalized units and the ratio of LFRRI/HFRRI will be used as a measure of sympatho-vagal balance. We will also calculate the standard deviation of normal-to-normal interval (SDNN) and the root mean square of successive differences (RMSSD) indexes, given their established study in PWE.[11, 12]

2. Cardiorespiratory Fitness:

a. Maximum oxygen uptake (VO₂ max)

i. Cardiopulmonary exercise test using a modified Balke protocol[55, 56] on a treadmill

b. 6-minute walk test (6MWT)

Participants will undergo a 6 minute walk test at Visits 1 and 3, according to established guidelines[57]. This is a cost-effective and well-documented field test for assessing functional exercise capacity and response to medical interventions in diverse patient groups, and predicts cardiorespiratory fitness among healthy people[58].

3. Sleep:

a. Nightly average total sleep time (TST): will be collected from the Garmin activity tracker

b. Sleep quality will be assessed via the Pittsburgh Sleep Quality Index (PSQI)

c.

Analytical Plan

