Human Subjects Protection

Subject Recruitment Methods

In order to ensure optimal recruitment, eligible subjects may be identified from the below recruitment pools. Potentially eligible subjects from the groups below will undergo further chart review to refine eligibility criteria by reviewing the following: age, epilepsy diagnosis, seizure type and frequency, ambulation status, medical history, and medications. In order to confirm eligibility of patients, the study team may review local charts or may ask the patient for copies of their local medical record (only the minimum amount of information will be collected by the study team to ensure a diagnosis of epilepsy).

Preliminarily eligible subjects will be contacted via telephone call from study staff, approached in person during their epilepsy clinic visit or EMU stay, or sent a message via mywakehealth. If the patient is not reached by phone, these individuals will receive, through mail, a letter from clinical PI asking them to contact us if interested in participating in the study. Once the patient is reached, a verbal screening consent will be obtained, allowing study staff to ask only screening questions including age, seizure frequency, ability to ambulate without difficulty, history of seizures associated with frequent falls or loss of muscle tone, current exercise habits, presence of end-stage CHF, ESRD, severe dementia, or presence of high blood pressure that is not controlled with medications (over 180/110) (Refer to phone screening script for further details). If contacted via an DComm approved message in mywakehealth, the participant can reach out to study staff via phone or email, or choose to click on a redcap link for more

Protocol version:

Template updated 9.24.14

information and to answer a small subset of preliminary screening questions (“do you have epilepsy” and “have you had at least 1 seizure in the past 6 months”). From here, preliminarily eligible participants will leave their contact information (phone number and/or email address) and, if eligible by chart review, subsequently be called by a member of the study team to perform the complete telephone screen.

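### The hypertension exclusion requires both blood pressure limits to be exceeded at once, so a resting 195/105 or 175/115 passes it before a maximal treadmill test; *and* should be *or*.

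*Combined protocol and SAP*

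**What the plan says.** Under Exclusion Criteria, one group is headed "Medical conditions that would limit ability to participate in an exercise intervention including", and its blood pressure entry defines uncontrolled hypertension as "systolic blood pressure greater than 180 mmHg and diastolic blood pressure greater than 110 mmHg at rest". No other numerical blood pressure limit appears among the criteria.

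Under Subject Recruitment Methods, the telephone screening questions cover "presence of high blood pressure that is not controlled with medications (over 180/110"). This repeats the two numbers without saying whether one or both must be exceeded.

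The visit schedule marks:
- eligibility review at Visit 0 (telephone) and Visit 1 (week 0);
- vital signs at Visit 1 and Visit 3 (week 16);
- the exercise test at Visit 2 (week 4) and Visit 3.

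A footnote to the schedule adds that, if scheduling is difficult, "V2 can be completed over the telephone with the exercise test being conducted at the first available timepoint and prior to the intervention period". The test is described under Outcome Measure(s), Cardiorespiratory Fitness, as "Cardiopulmonary exercise test using a modified Balke protocol[55, 56] on a treadmill", with maximum oxygen uptake as the measure.

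**The concern.** An upper blood pressure limit for an exercise study is meant to keep out anyone whose systolic or diastolic pressure is dangerously high. Joining the limits with *and* makes each one conditional on the other. One component can then be raised to any level without triggering the exclusion, provided the other stays at or below its own limit.

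Participant safety is at stake. The protocol's Background describes cardiovascular comorbidity in up to 80% of people with epilepsy, with raised rates of arrhythmia, myocardial infarction and premature death. The criteria then select people who are not very active, and the schedule gives them a maximal treadmill test. If the stated rule is followed literally, a person with a severe elevation of one component can reach that test as an eligible participant.

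**Working it through.** The plan gives no figure to reproduce. The check has three parts: the logic of the criterion, a search for another safeguard, and a rough size.

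**1. The criterion as logic.** The inputs are the limits in the Exclusion Criteria, systolic (SBP) above 180 mmHg and diastolic (DBP) above 110 mmHg.

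- As written, a person is excluded if SBP > 180 and DBP > 110. A person passes if either pressure is at or below its limit.
- With *or*, a person is excluded if SBP > 180 or DBP > 110. A person passes only if both pressures are at or below their limits.

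| Resting pressure | SBP > 180 | DBP > 110 | Excluded as written (*and*) | Excluded with *or* |
|---|---|---|---|---|
| 195/115 | yes | yes | yes | yes |
| 195/105 | yes | no | no | yes |
| 175/115 | no | yes | no | yes |
| 175/105 | no | no | no | no |
| 220/110 | yes | no | no | yes |
| 180/130 | no | yes | no | yes |

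Three patterns have at least one limit exceeded: both, systolic only and diastolic only. The present wording excludes the first; *or* excludes all three. This counts patterns, not people.

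**2. Whether another rule closes the gap.**

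- *Telephone screen.* It relies on the person's own report, and its shorthand can be read either way. It neither corrects nor contradicts the criterion.
- *Visit 1.* Vital signs and eligibility review coincide here, so this is where the criterion is applied to a measured pressure. A reading of 195/105 does not meet the definition.
- *Visit 2.* The exercise test is marked, but vital signs and eligibility review are not. The last scheduled reading is from week 0 and the test is at week 4, so the reading is 4 − 0 = 4 weeks old. It is older if Visit 2 is held by telephone and the test follows later. The protocol also warns that batched enrollment can change the time between visits.
- *The test itself.* The description names the treadmill protocol and gives no blood pressure limit for starting.

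**3. Rough size.** The documents do not say what share of participants would exceed exactly one limit. Call it p and assume 0.5% to 2%. The enrollment cap is n = 40. The expected number is 40p, and the chance of at least one is 1 − (1 − p)^40.

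| p (assumed) | Expected number, 40p | Chance of at least one |
|---|---|---|
| 0.005 | 0.2 | 1 − 0.995^40 = 0.182 |
| 0.01 | 0.4 | 1 − 0.99^40 = 0.331 |
| 0.02 | 0.8 | 1 − 0.98^40 = 0.554 |

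**The case against.** The strongest reply is that the blood pressure entry is not the only safeguard. Its parent heading is open-ended, chart review covers medical history and medications, and vital signs are taken at the visit where eligibility is reviewed. A sensible investigator would probably not send someone at 195/105 to a treadmill, and may well read the telephone shorthand as applying to either component. This stands in part: the plan permits exclusion on judgement. It does not require it, and because hypertension is given its own explicit definition, staff following that definition would find the person eligible.

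Second, the intended connective is nowhere stated, so preferring *or* is a safety judgement. That is true. However, the documents give no reason for requiring both elevations, and a rule that passes 220/110 does not serve its heading. The activity exclusion in the same criteria joins its two limits with *or*.

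Third, an exercise laboratory may check blood pressure on the day whatever the protocol says. That is possible. The documents support only the statement that no pre-test limit is written down, not that no check takes place.

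Fourth, the age of the last reading is a separate matter, since it would be just as old under *or*. This is right. The timing shows that no later written step catches what the criterion lets through, but the wording error does not depend on it.

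Fifth, the assumed 0.5% to 2% has no source in the documents. It also ignores the selection already made by chart review and the telephone screen, and 40 is a cap. All of this stands. The range only illustrates that the number is small.

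**Conclusion.** The concern holds. Read literally, the only stated blood pressure limit does not exclude a person with a severe elevation of one component, however high, and no other written rule does so before the first maximal treadmill test. This conclusion rests on the wording and the schedule alone.

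The practical size is probably small. Under the assumed range, fewer than one affected participant is expected among 40. Calling *or* the right connective is a clinical safety judgement, although the alternative is hard to defend. The effect is confined to eligibility and safety: neither the primary adherence and sustainability estimates nor the sample size depends on it. The correction is worth making because the possible harm is serious and the change costs almost nothing.

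**What to change.** 1. In the Exclusion Criteria, define uncontrolled hypertension as a resting systolic pressure above 180 mmHg **or** a resting diastolic pressure above 110 mmHg. Apply this at the Visit 1 vital-sign check.
2. Word the telephone screening question the same way, so that a report of either pressure above its limit counts.
3. As a useful addition, record a resting blood pressure immediately before the first exercise test, whether at Visit 2 or on the later date if Visit 2 is by telephone. Do not start the test if either limit is exceeded. If the exercise laboratory already does this, the protocol need only say so.

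The cost is one word in the criterion, one matching phrase in the telephone screen and one reading before the treadmill test. On the assumed range, the extra exclusions would most likely be none or one among up to 40 participants. At the top of the range (2%), the chance of none is 1 − 0.554 = 0.446, and the chance of exactly one is 40 × 0.02 × 0.98^39 = 0.364, so none or one has a chance of 0.446 + 0.364 = 0.81.
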